7.14 Cerebrospinal Fluid Opening Pressure Measurement

A CSF opening pressure measurement (cm of H₂O) will be conducted as per standard hospital practice. The measurement will be obtained whenever a LP is performed and an IDDD revision or replacement is done. Following implementation of Amendment 6 the CSF opening pressure measurement will not be required with the LP.

7.15 Dispensing Study Drug

A visual examination of both the port and catheter track will be performed before each IT injection.

HGT-1410 will be administered IT by means of an IDDD (or via LP if necessary) to patients on Day 2 (± 2 days) of Week 1 of each treatment month.

The patient may be sedated for this procedure. HGT-1410 will be administered through an appropriately sized syringe (see the Pharmacy Manual). If the IT space is not accessible via the IDDD, HGT-1410 may be administered via LP. See Section 6.3.2 for details.

For the Soph-A-Port Mini S, a 22-gauge Huber non-coring needle is to be used for access to the implanted port; standard hypodermic needles would damage the septum and may cause leakage. If no needle-free connector is present, either a stopcock or the Huber needle infusion set's clamp is to be used to prevent CSF backflow and to mitigate the risk of air entering the system. It is possible to use other brands of Huber non-coring needles, provided that their specifications are identical to that of the Huber needle supplied by Sophysa in the SOPH-A-PORT Mini S (22G).

7.16 Pharmacokinetic Assessments

Pharmacokinetic assessments are not included in this study.

7.17 Neurological Examination

A neurological examination to monitor CNS changes in a patient's neurological status will be conducted during this study. See [Appendix 2](#) for a complete list of the neurological examinations.

The neurological exam should not occur sooner than 4 hours after study drug administration or before the patient has fully recovered from any anesthesia administered for the dosing, whichever occurs later.

7.18 Neurocognitive and Developmental Assessments

Patients will undergo neurocognitive and neurobehavioral development testing. The assessments are estimated to last between 2 and 4 hours and must be conducted prior to sedation or anesthesia.

A full neurodevelopmental assessment, including global development, cognition, adaptive behavior, receptive and expressive language, and gross motor function, will be evaluated using standardized developmental and behavioral tests to provide a surrogate and quantifiable measure of global CNS neurodevelopmental/neurobehavioral function.

All patients will have received a series of standardized neurodevelopment assessments; in the HGT-SAN-055 study, patients in HGT-SAN-067 will continue with the age specific assessment they began with in HGT-SAN-055. If, however, a patient's capability improves and they become capable of completing assessments at a higher level, any such additional assessments may be added. Any additional assessments would be performed after the original assessments have been carried out.

For this study, outcome measures will be computed for each patient enrolled. The psychometric instruments and Sanfilippo-specific assessments are summarized below in [Table 7-1](#) and [Table 7-2](#), respectively. See [Appendix 2](#) for details on these assessments.

Table 7-1 Neurodevelopmental Assessments Tests

Developmental or Cognitive Domain(s)	Patient Age: Representative Cognitive Test or Scale
COGNITIVE DEVELOPMENT ASSESSMENT	
Summary score and sub-domains: - Cognitive - Motor - Social/emotional	0 to 42 months: Bayley Scales of Infant Development-III Bayley Scales of Infant Development, Third Edition (BSID-III) ²³
- Cognitive - Processing skills	3 to 18 years: Kaufman Assessment Battery for Children, Second Edition (KABC-II) ²⁴

Table 7-1 Neurodevelopmental Assessments Tests

Developmental or Cognitive Domain(s)	Patient Age: Representative Cognitive Test or Scale
GROSS AND FINE MOTOR SKILLS ASSESSMENT AND VOLUNTARY MOVEMENT	
Motor	3.0 to 16:11 years: Movement Assessment Battery for Children II (MABC-2) ²⁵
- Cognitive	0 to 5 ½ years: Bayley Scales of Infant Development III
- Motor	(BSID-III) ²³
ADAPTIVE BEHAVIOR	
Communication	0 to 90 years: Vineland Adaptive Behavior Scales (VABS-II)
Daily Living	Second Edition ²⁶
Socialization	
Motor Skills	

Table 7-2 Sanfilippo-Specific Disability Assessment And Behavior Rating Scales

DEVELOPMENTAL OR COGNITIVE DOMAIN(S)	SANFILIPPO SPECIFIC ASSESSMENTS
Parent-scored behavioral inventory	Sanfilippo Behavior Rating Scale (SBRS)
- communication: understanding	
- communication: expression	
- tantrums	
- specific behaviors inventory	
- mood & emotions inventory	
MPS-specific disability score	Four-Point Scoring System/Total Disability Score
- cognitive functioning	(FPSS/TDS) ⁵
- expressive language	
- motor score	

7.19 Sleep Questionnaire: Children’s Sleep Habits Rating Scale

A sleep questionnaire, Children’s Sleep Habits Rating Scale, will be administered to the patient's parent(s)/legally authorized representative(s).

7.20 Age-Dependent, Health-Related Quality of Life in Children

The Quality of Life questionnaires will be administered as outlined in Sections [7.20.1](#), [7.20.2](#), and [7.20.3](#).

7.20.1 Quality of Life Indicator: CHQ-50

The Child Health Questionnaire™ Parent Form 50 Questions (CHQ-50) will be administered during the study. The questionnaire is a generic quality of life instrument, measuring 14 unique physical and psychosocial concepts, which was developed for children from 5 to 18 years of age.

7.20.2 Quality of Life Indicator: CHQ-87

The Child Health Questionnaire™ Child Form 87 (CHQ-87) will be administered during the study. The CHQ-87 is a child and adolescent self-report, developed for ages 10 and older, which assesses the child's self-perceived physical and psychosocial well-being.

7.20.3 Quality of Life Indicator: ITQOL

The Infant Toddler Quality of Life Questionnaire™ (ITQOL) will be administered during the study. The ITQOL was developed for children at least 2 months of age up to 5 years and assesses the physical, mental, and social well being of the child and assesses the quality of the parent/legally authorized representative(s) life.

7.21 Concomitant Medications, Therapies and Medical/Surgical Procedures

All non-protocol treatments that occur from the time of informed consent (and assent, if applicable) through the safety follow-up contact are regarded as concomitant and will be documented on the appropriate pages of the eCRF. Concomitant therapy includes medication (including Genistein), therapies/interventions administered to patients, and medical/surgical procedures performed on the patients.

Every effort should be made to keep symptomatic Sanfilippo syndrome Type A treatment constant throughout the study. However, changes in medications are acceptable if necessary according to clinical judgment. All changes will be recorded on the appropriate eCRF. Concomitant medication will be coded using WHO-DD.

7.22 Adverse Events

7.22.1 Definitions of Adverse Events and Serious Adverse Events

7.22.1.1 Adverse Event

An AE is any noxious, pathologic, or unintended change in anatomical, physiologic, or metabolic function as indicated by physical signs, symptoms, or laboratory changes occurring in any phase of a clinical study, whether or not considered study drug-related. This includes an exacerbation of a pre-existing condition. Once the informed consent is signed and dated, any adverse event prior to the start of study drug must be reported.

AEs include:

- Worsening (change in nature, severity, or frequency) of conditions present at the onset of the study
- Intercurrent illnesses
- Drug interactions

- Events related to or possibly related to concomitant medications
- Abnormal laboratory values (this includes significant shifts from baseline within the range of normal that the investigator considers to be clinically important)
- Clinically significant abnormalities in physical examination, vital signs, and weight

Throughout the study, the investigator must record all AEs on the AE eCRF, regardless of the severity or relationship to study drug. The investigator should treat patients with AEs appropriately and observe them at suitable intervals until the events stabilize or resolve. AEs may be discovered through observation or examination of the patient, questioning of the patient, complaint by the patient, or by abnormal clinical laboratory values.

In addition, AEs may also include laboratory values that become significantly out of range. In the event of an out-of-range value, the laboratory test should be repeated until it returns to normal or can be explained and the patient's safety is not at risk.

All AEs should be recorded with causality assessment.

The information presented below is intended to provide issues to consider for AEs associated with intrathecal injections of HGT-1410. In general, these AEs can be classified as follows:

- Adverse events due to systemic exposure to HGT-1410 caused by the drug diffusion from the CSF to the peripheral circulation;
- Adverse events related to the direct delivery of HGT-1410 to the intrathecal CSF space and meninges, and subsequent diffusion into brain parenchyma, via an intrathecal route
- IDDD-related AEs

Note: the classification of potential AEs and the examples presented below are based on purely theoretical considerations and/or published literature as there is limited human experience with intrathecal HGT-1410 therapy to date.

7.22.1.2 Potential Adverse Events: Intrathecal recombinant human heparan N-sulfatase

ADVERSE EVENTS RELATED TO THE DIRECT DELIVERY OF HGT-1410 TO THE CNS THROUGH INTRATHECAL ADMINISTRATION

Examples of AEs observed in other published clinical trials with intrathecally-administered peptides or proteins, include, but are not limited to the following: headache, fever, feeling of warmth, sensory paresthesias (including feelings of warmth, tingling, or pain) or autonomic symptoms such as dry mouth or gustatory abnormalities (including loss of smell and metallic taste). Changes in mental cognitive status or level of consciousness that are not caused by pre-medication may either occur acutely or develop post-injection, over time.

ADVERSE EVENTS DUE TO SYSTEMIC EXPOSURE TO HGT-1410

Although HGT-1410 is given intrathecally only, some proportion of the drug will diffuse from the CSF into the peripheral circulation. The resulting systemic exposure may cause events that

are typically seen in patients receiving ERT via an intravenous administration, known as infusion-related reactions. An infusion-related reaction is defined as an adverse event that (1) begins either during or within 24 hours after the start of the infusion, and (2) is judged as possibly or probably related to study drug. Other AEs that occur prior to the infusion, along with AEs associated with protocol-defined testing and assessments (laboratory testing and physical examinations) that were performed prior to the infusion will not be defined as infusion-related reactions.

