7.22.3 Classification of Adverse Events and Serious Adverse Events

The National Cancer Institute Common Terminology Criteria for Adverse Events (NCI CTCAE) version 3.0 grading scale should be referenced when assessing the severity of an AE (see [Appendix 6](#)). If an AE is not described in the NCI CTC, the severity should be recorded based on the scale provided in [Table 7-3](#). The severity of all AEs/SAEs should be recorded on the

appropriate eCRF page. Adverse events are graded as Grade 1, 2, 3, 4, or 5 corresponding, respectively, to a severity of mild, moderate, severe, life-threatening, or death.

Table 7-3 Adverse Event Severity

Severity	Definition
Grade 1 (Mild)	No limitation of usual activities.
Grade 2 (Moderate)	Some limitation of usual activities.
Grade 3 (Severe)	Inability to carry out usual activities.
Grade 4 (Life-threatening)	Immediate risk of death.
Grade 5 (Death related to an AE)	Death

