7.22.4 Relatedness of Adverse Events and Serious Adverse Events

Relationship of an AE or SAE to investigational product, device, device surgical procedure, or IT administration process is to be determined by the investigator based on the definitions in [Table 7-4](#):

Table 7-4 Adverse Event Relatedness

Relationship to Product(s)	Definition
Not Related	Unrelated to study drug, device, device surgical procedure, or IT administration process.
Possibly Related	A clinical event or laboratory abnormality with a reasonable time sequence to administration of study drug, device, device surgical procedure, or IT administration process but which could also be explained by concurrent disease or other drugs or chemicals.
Probably Related	A clinical event or laboratory abnormality with a reasonable time sequence to administration of study drug, device, device surgical procedure, or IT administration process unlikely to be attributable to concurrent disease or other drugs and chemicals and which follows a clinically reasonable response on de-challenge. The association of the clinical event or laboratory abnormality must also have some biologic plausibility, at least on theoretical grounds.
Definitely Related	The event follows a reasonable temporal sequence from administration of the medication, device, device surgical procedure, or IT administration process follows a known or suspected response pattern to the medication, is confirmed by improvement upon stopping the medication (dechallenge) and reappears upon repeated exposure (rechallenge). Note that this is not to be construed as requiring re-exposure of the patient to study drug; however, the determination of definitely related can only be used when recurrence of event is observed.

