7.24 Safety-related Study Stopping Rules

If any patient experiences a life-threatening (Grade 4) adverse event or death which is considered by the sponsor to be possibly, probably, or definitely related to study drug **or the IDDD**, or if 2 or more patients experience a Grade 3 adverse event during the trial that is considered by the sponsor to be possibly, probably, or definitely related to the study drug **or the IDDD**, then the site will be instructed to halt further HGT-1410 administration to all patients and the safety data reviewed. Following a review of safety data, the study will be either:

- Resumed unchanged
- Resumed with modifications to the protocol or
- Terminated

Patient safety will be monitored on a continuous basis during this study until the last patient completes his or her last scheduled study visit/assessment.

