10.6 Efficacy, Safety, and Pharmacodynamic Evaluations

10.6.1 Primary Analyses

10.6.1.1 Safety Analysis

In general, safety assessments will be based on all assessments post-baseline. The assessment of safety will be based primarily on the frequency of AEs, and on the frequency of clinically notable abnormal vital sign and laboratory values. Changes from baseline will be calculated by subtracting the baseline value from the post-baseline value.

All enrolled patients who had an IDDD surgical procedure and/or received administration of HGT-1410 will be included in the safety analysis.

Adverse events will be recorded throughout the study and at early termination. Adverse events and medical conditions will be coded using the Medical Dictionary for Regulatory Activities (MedDRA).

Adverse events will be summarized by presenting, for each dose group during the treatment period, the number and percentage of patients having any AE, having an AE in system organ class, and having each individual AE. In addition, those events which resulted in death or were otherwise classified as serious will be presented in a separate listing. The incidence of treatment-emergent adverse events, defined as all AEs from the time of the surgery for IDDD implantation to the last follow up contact, ie, 30 days after the last HGT-1410 administration, (new or worsened from baseline) during the treatment period, will be summarized by system organ class, severity, type of adverse event and relationship to trial medication/procedure.

Treatment-emergent AEs, of the treatment period, deemed related to HGT-1410 administration will be summarized separately.

IDDD and procedure-related AEs will be summarized within system organ class by preferred term. IDDD and procedure-related AEs will be tabulated by severity (mild, moderate, severe) and degree of relatedness. Separate tabulations will be provided for adverse events related to the IDDD, device surgical procedure (including post-implant infections) and IT administration process. These summaries will be presented by device and overall, as appropriate.

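### The infusion-related reaction definition omits definitely related events, and the device adverse-event table has no rows for Grades 4 and 5

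*Protocol*

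**What the plan says.** **Infusion-related reactions.** Protocol Section 7.22.1.2 sets two conditions. The event must begin during the infusion or within 24 hours of its start, and it must be one that "is judged as possibly or probably related to study drug".

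**Relatedness scale.** Table 7-4 in Section 7.22.4 has four levels: not, possibly, probably and definitely related. Its note on the top level says that "the determination of definitely related can only be used when recurrence of event is observed".

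**Severity scale.** Section 7.22.3 states: "Adverse events are graded as Grade 1, 2, 3, 4, or 5 corresponding, respectively, to a severity of mild, moderate, severe, life-threatening, or death".

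**Device and procedure table.** Section 10.6.1.1 states: "IDDD and procedure-related AEs will be tabulated by severity (mild, moderate, severe) and degree of relatedness".

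**Stopping rule.** Section 7.24 acts on a life-threatening (Grade 4) event or a death that is "considered by the sponsor to be possibly, probably, or definitely related to study drug" or to the device. It has a separate trigger for Grade 3 events in two or more patients.

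**The concern.** Long-term safety is the primary endpoint (Section 3.1), and adverse events enter it by type and severity. The analysis is descriptive (Section 10.1), so the categories and counts are the result. No test or model stands behind them to absorb a faulty category.

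Two categories do not match the protocol's own scales. The infusion-related reaction definition stops one level short of the relatedness scale, and the missing level is the one that requires the event to be seen again. With dosing every 28 days (Section 6.3) for up to 8 years (Section 4.3), recurrence is something this study can observe. The label is thus withheld from the reactions for which the causal evidence is strongest.

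The device table stops two grades short of the severity scale. Whoever programs it must either fold Grades 4 and 5 into severe or leave them out, and the text does not say which. The protocol foresees such events: Appendix 3 lists meningitis, encephalitis and paralysis among expected device effects, and Section 7.22.1.4 names death among the risks of anesthesia.

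**Working it through.** The plan gives no figure to reproduce, and no sample-size or power formula applies. The check compares sets of categories.

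**Step 1: relatedness.**

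| Level in Table 7-4 | Infusion-related reaction (7.22.1.2) | Stopping rule (7.24) |
|---|---|---|
| Not related | no | no |
| Possibly | yes | yes |
| Probably | yes | yes |
| Definitely | **no** | yes |

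The definition covers 2 of the 3 related levels: 3 − 2 = 1 is missing, the strongest.

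**Step 2: what that does to a count.** Suppose a patient has k reactions inside the 24-hour window, all judged related to study drug, and d of them are rated definitely related.

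- Events labelled as infusion-related reactions under the literal text: k − d. The shortfall is d events.
- Patients with at least one such reaction: this patient still counts while k − d is at least 1. Because the definite rating needs an observed recurrence, the first reaction is rated possibly or probably related when it occurs, so k − d is at least 1 unless that first event is re-rated later. The protocol prescribes no such re-rating.

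The gap therefore lowers a count of events but ordinarily leaves the number of patients affected unchanged.

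**Step 3: severity.**

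| Grade (7.22.3) | Named level in the device table (10.6.1.1) | Stopping rule (7.24), if related |
|---|---|---|
| 1 mild | yes | no trigger |
| 2 moderate | yes | no trigger |
| 3 severe | yes | two or more patients |
| 4 life-threatening | **no** | any one patient |
| 5 death | **no** | any one patient |

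The table names 3 of the 5 grades: 5 − 3 = 2 are missing. The stopping rule treats Grade 4 and death differently from Grade 3, so a device table that cannot separate them cannot be reconciled with it.

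**Step 4: where the same events do appear.**

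- Section 7.22.1.1: "the investigator must record all AEs on the AE eCRF, regardless of the severity or relationship to study drug".
- Section 10.6.1.1, general summary: treatment-emergent events "will be summarized by system organ class, severity, type of adverse event and relationship to trial medication/procedure", with no level left out. Those related to HGT-1410 are also summarized separately.
- Section 10.6.1.1: deaths and other serious events are listed separately. Section 7.22.1.5 makes every fatal or life-threatening event serious.
- Section 7.24: definitely related events, Grade 4 events and deaths all count.

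**Step 5: relatedness in the device table.** That table is already split by degree of relatedness with no level excluded, so definitely related is not missing there.

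**The case against.** The strongest reply has four parts.

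1. *The events are captured elsewhere.* This stands. A reader might infer that the most certain and the gravest events have no place in the safety classification. The documents do not support that, because every route in step 4 of the working remains open.

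2. *There is no infusion-reaction count to distort.* Section 10 names no table of infusion-related reactions, and Section 3.1 does not list them as an endpoint. Section 7.22.1.1 presents the surrounding material as considerations that are largely theoretical, and management in Section 7.22.1.3 turns on a suspected reaction, not on this label. This also stands, and it limits the point to the label and to any count later built on it. It does not make the definition right: an analyst who needs such a count will take the protocol's definition.

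3. *Patient-level incidence would not move.* A reader might infer that a patient with repeated reactions drops out of the count, and that in a study of at most 12 patients (Section 10.2) this shifts a group percentage a long way. That does not follow, because the first reaction already qualifies the patient (step 2). The shortfall is in events.

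4. *Table layout belongs to the statistical analysis plan.* Section 10.6.4 does leave the final presentations to that plan, which is not at hand. But the protocol is not silent here. It names three levels, and they contradict its own scale of "a severity of mild, moderate, severe, life-threatening, or death". That is a stated rule which conflicts with another, not a detail left open.

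**Conclusion.** The point holds in a narrow form. There are two inconsistencies in the current text:

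- The infusion-related reaction definition leaves out 1 of 3 related levels. Read literally, recurrences confirmed on re-dosing lose the label, and any event count based on it is too low by the number of such recurrences. The documents give no means of estimating that number.
- The device and procedure table leaves out 2 of 5 severity grades. Life-threatening and fatal device events are either merged with Grade 3 or absent from that table.

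This rests on reading both sentences literally and on the definite rating being used as Table 7-4 prescribes. The harm is confined to one label and one table. It is still worth correcting, because these are safety classifications in a study whose primary endpoint is safety.

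**What to change.** - **Section 7.22.1.2:** extend the relatedness condition to possibly, probably, or definitely related, in line with Table 7-4 and Section 7.24.
- **Section 10.6.1.1:** replace the three severity levels for IDDD and procedure-related events with Grades 1 to 5 as in Section 7.22.3.

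No change to the relatedness split of the device table is needed. It already runs by degree, and a not-related row would make no sense in a table of related events.

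The cost is two wording changes and two more rows in one set of tables. All grades and relatedness levels are already collected, so no new data are needed and no clinical rule changes.
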